13. DATA ANALYSIS AND MONITORING

13.1. Sample Size Justification

The study will recruit 36 total subjects to accrue 30 fully evaluable subjects with an estimated 20% withdrawal rate. The target enrollment table in §3.9 shows that we have access to enough eligible patients to complete this study in 12 months. The following table shows the

Page 33 of 41 RSRB STUDY00004587 Version Date: 09/14/2021 NCT04238728 precision estimates and 95% confidence intervals for our primary objective (i.e., adverse events related to Silverlon®) and secondary objective (i.e., compliance and withdrawal rate). Our estimates for adverse events (primary and intent to treat analyses) are based on published trials showing no reported adverse events or allergic reactions to silver nylon dressing in patients receiving radiation (8, 15-17). Our estimates for the primary objective were conducted with sample size of 30 for the fully evaluable subjects and 36 for all subjects that initiated treatment. Our estimates for compliance (secondary analyses) are based on the Aquinos-Parsons et al study in breast cancer patients that showed a 97% compliance rate for silver nylon dressing (8). Our estimates for compliance were conducted using sample size of 30 for fully evaluable subjects. In subjects that withdraw from the study, we will be able to partially evaluate compliance because of their early termination of treatment and study procedures. Our estimates for withdrawal are based on the Vavassis et al study in head & neck cancer patients using silver nylon dressing that reported 1 of 12 subjects (i.e., 8%) withdrew from the study (17). Our estimates for withdrawal were conducted using a sample size of 36 to capture all subjects that initiated treatment. 95% Exact Clopper Pearson confidence intervals on the expected proportion have been generated using SAS 9.4.

95% Confidence Intervals								
Objective	Measure	Sample Size	Proportion Estimate	Expected Observed Count	95% LCL	95% UCL		
Primary	# Adverse Events per number of patients	30	0	0	0	0.116		
Intent to Treat	# Adverse Events per number of patients	36	0	0	0	0.097		
Secondary	Compliance	30	0.97	29	0.828	0.999		
Secondary	Withdrawal	36	0.166	6	0.064	0.328		

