13.2. Statistical Analyses

This is a safety study to determine Silverlon® dressing indication for radiation dermatitis. Descriptive statistics will be used to describe the study subject population. The primary analyses will evaluate the number of adverse events or reactions reported (if any) at the breast irradiation site where the Silverlon® dressing was applied. The primary analyses will be conducted on 30 fully evaluable subjects (i.e., 30 subjects that fully complete the study) and on all subjects that initiated treatment with Silverlon® dressing in an intent to treat analysis (see section 13.1). For a safety study, it is important to obtain the overall adverse event rate for all subjects that initiated treatment and all subjects who fully completed the study.

The secondary analyses will evaluate the compliance rates for the Silverlon® Dressing during RT and post RT. Compliance will be on the number of days during RT and post-RT that the dressing was worn. We expect compliance rate to be 97% (8). Additionally, we will evaluate the percentage of subjects that removed the dressing for sleeping. Subjects are asked to wear the dressing during sleep and only remove the dressing for RT sessions, showering/bathing, or swimming. Furthermore, we will calculate the number of hours during a day that the dressing was not worn summing the time between removal and application of the dressing each day.

Page 34 of 41 Version Date: 09/14/2021 Compliance will be evaluated in the 30 fully evaluable subjects. Although we can and will evaluate compliance in all subjects that initiated treatment, these analyses will not provide a complete picture of compliance due to early termination of study procedures. Furthermore, the secondary analyses will also evaluate withdrawal rates due to the Silverlon® dressing in all subjects who initiated treatment. We expect less than 6 subjects to withdraw due to the Silverlon® dressing. The exploratory analyses will assess trends in radiation dermatitis severity (i.e., RTOG and RISRAS) and quality of life (DLQI) during the course of the study. These analyses will also be able to evaluate changes in skin symptoms experience by the patient based on the RISRAS-Patient Symptom Scale during RT.

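### Section 13.1 states compliance precision for a share of subjects (29/30), but 13.2 measures days worn, so the printed interval does not describe the planned measure, and the lead set is selected partly on adherence

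*Combined protocol and SAP*

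**What the plan says.** **Precision (13.1).** The section states "Our estimates for compliance were conducted using sample size of 30 for fully evaluable subjects" and "95% Exact Clopper Pearson confidence intervals on the expected proportion have been generated using SAS 9.4". The compliance row reads n = 30, proportion 0.97, expected count 29, limits 0.828 and 0.999. The 97% comes from a cited breast cancer study of silver-nylon dressing. On subjects who leave early, it says "we will be able to partially evaluate compliance because of their early termination of treatment and study procedures".

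**Analysis (13.2).** The section states "The secondary analyses will evaluate the compliance rates for the Silverlon® Dressing during RT and post RT", gives the measure as "Compliance will be on the number of days during RT and post-RT that the dressing was worn" and expects the same 97%. It then says "Compliance will be evaluated in the 30 fully evaluable subjects". It adds that all initiators will also be analysed, but calls that picture incomplete because of early termination. Two further wear measures are planned: the percentage of subjects who take the dressing off to sleep, and, in its words, "we will calculate the number of hours during a day that the dressing was not worn summing the time between removal and application".

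**Who is in the set.** Section 3.1 defines a fully evaluable subject partly by continuing the dressing to two weeks after radiation therapy (RT). Section 7 allows withdrawal for non-compliance, gives no cut-off, and replaces withdrawn subjects.

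**What is collected.** Sections 5.3 and 5.4 describe a log of every removal and re-application, with times and a reason.

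**The concern.** The planned precision and the planned analysis use different units. A binomial interval on 29 of 30 needs each subject classed as compliant or not. Days worn gives each subject a number between 0% and 100%, and the plan has no rule that turns one into the other. The reported rate therefore cannot be set against the stated interval, and the choices that determine it could be made after the data are seen.

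The second issue is who leads the analysis. A subject who stops wearing the dressing cannot be a completer, and one withdrawn for non-compliance is replaced by someone else. The lead set is thus selected partly on the outcome being measured, which tends to push the rate up.

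Compliance is one of two secondary outcomes and carries much of the feasibility objective in section 1.3, so its definition should be fixed in advance.

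**Working it through.** **1. The plan's own figure.** Inputs from 13.1: x = 29, n = 30, exact two-sided 95%.

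- Lower limit: Beta quantile (0.025; x, n − x + 1) = Beta(0.025; 29, 2) = 0.828.
- Upper limit: Beta quantile (0.975; x + 1, n − x) = Beta(0.975; 30, 1) = 0.999.

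This matches the table. A non-integer count of 29.1 would give a lower limit of 0.833, so the row rests on a whole number of subjects, 29 out of 30.

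**2. An interval that fits days worn.** For the mean per-subject percent of days worn, the half-width is t(0.975, n − 1) × SD / √n. The documents give no SD, so a range is assumed. With n = 30, t/√n = 2.045/5.477 = 0.373.

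| Assumed SD (points) | Half-width (points) | Interval around 97% |
|---|---|---|
| 3 | 1.1 | 95.9 to 98.1 |
| 5 | 1.9 | 95.1 to 98.9 |
| 10 | 3.7 | 93.3 to 100 (capped) |

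These are approximate, because the data will be skewed near 100%.

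**3. How far the two measures can part.** Section 3.5 allows 15 to 40 fractions. Assuming 5 fractions a week and adding the 14 post-RT days, a subject has about 35 to 70 days of wear. If every subject misses exactly one day:

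- Days-based rate: 34/35 = 97.1% to 69/70 = 98.6%.
- Share of compliant subjects: 0/30 if every day is required, 30/30 if 90% of days is required.

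That pattern is artificial, so here are two less extreme models, both with 97% of days worn.

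*Days independent, each worn with probability 0.97 (assumption): expected compliant subjects out of 30.*

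| Share of days required | 35 days | 70 days |
|---|---|---|
| 80% | 30.0 | 30.0 |
| 90% | 29.4 | 30.0 |
| 95% | 21.5 | 25.2 |
| 100% | 10.3 | 3.6 |

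*Per-subject share beta-distributed, mean 0.97, SD 3 to 10 points (assumption):* the compliant share is 95% to 99.9% at a threshold of 80% of days, 92% to 96% at 90%, and 80% to 88% at 95%.

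**4. The lead set.** Take 29 of 30 completers as compliant and the 6 withdrawals in the 13.1 table. The completer rate is 29/30 = 96.7% whatever the six did. The all-initiator rate depends on how many of the six were non-compliant before leaving, which the documents do not predict:

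| Non-compliant among the 6 (assumed) | All initiators |
|---|---|
| 0 | 35/36 = 97.2% (exact 95% interval 0.855 to 0.999) |
| 1 | 34/36 = 94.4% |
| 2 | 33/36 = 91.7% |
| 3 | 32/36 = 88.9% |

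**The case against.** The best defence is that little turns on this. The interval is a planning figure, 13.2 sets no test or success threshold for compliance, and it does not promise an interval in the report. The plan also gives more than one view of wear: separate RT and post-RT rates, removal for sleep, hours not worn and an all-initiator analysis. A subject who leaves the dressing off at night would show up in two of these. All of that stands, and it limits the severity. It does not supply a link between days and compliant subjects, or a denominator for those who leave early.

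A reader might go further in four ways that the documents do not support.

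- *That the interval is wrong or precision is overstated.* It reproduces exactly. It is attached to the wrong measure, and at the SDs shown an interval for a mean would be narrower.
- *That the 97% is wrong.* The documents do not say whether the cited study's figure is a share of subjects or of days, so no error in the value follows.
- *That a thresholded share of subjects must be the lead measure.* That is a preference. A threshold discards information, and keeping days worn cures the mismatch equally well.
- *That 5.1 contradicts 5.2 and 6.1 on topical agents.* Section 5.1 defers to sections 5.2 and 6.0 on this, and 5.2 and 6.1 agree on removal and re-application.

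**Conclusion.** The mismatch is established from the text alone: a subject-level binomial interval in 13.1, a days-worn measure in 13.2, and nothing joining them. The risk of upward bias in the lead set follows from sections 3.1 and 7. Its direction is clear, but its size is not known. The drop from 97.2% to 88.9% across the cases shown rests on assumed behaviour among six withdrawals. The half-widths rest on assumed SDs, and the threshold results on assumed wear patterns and a five-fraction week.

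Severity is minor. Precision is misdescribed, the outcome is descriptive and secondary, and n = 30 does not depend on it.

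**What to change.** Make the precision row and the analysis use the same measure, by one of two routes:

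- **(a) Keep days worn.** Report the mean per-subject percent of days worn, separately for RT and post-RT, and replace the 13.1 row with an interval for a mean. For 36 initiators the multiplier is 2.030/6 = 0.338, giving half-widths of about 1.0, 1.7 or 3.4 points at SDs of 3, 5 or 10.
- **(b) Keep the Clopper-Pearson interval.** State in advance the share of days that makes a subject compliant.

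Either route needs a sentence saying how log times make a day count as worn. Under both, lead with all who initiated treatment, counting each subject's days up to withdrawal, and keep the 30 completers as supportive. Under (b) the rows become 35/36 (0.855 to 0.999) and 29/30 (0.828 to 0.999). Use the reasons already on the log to split hours not worn into permitted and other removals.

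Separately, two sets of passages must be reconciled; this review does not say which is right.

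- *Start day:* section 4 differs from 2.1, 5.1 and 5.2. This also bears on section 1.3, which expects a compliance rate before RT that 13.2 does not count.
- *Permitted removals:* swimming is missing from the wear instruction in 5.1 but present in 5.2, 5.3 and 13.2, and removal for topical agents is missing from the 13.2 list.

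The cost is a few sentences in section 13 and slightly more log processing, with no new data. The downsides are a rate that may fall below 97% and, under (b), a threshold that must be justified beforehand.

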3. CHARACTERISTICS OF RESEARCH POPULATION

3.1. NUMBER OF SUBJECTS

This is a single site study at the University of Rochester Medical Center, with an accrual goal of 30 fully evaluable subjects. "Fully evaluable" as defined as completing informed consent, meeting eligibility criteria, initiating Silverlon® dressing during radiation therapy and continuing to two weeks after completion of radiation therapy. Therefore, the 30 fully evaluable subjects must complete full protocol procedures. Assuming a 20% withdrawal rate, we will recruit 36 eligible subjects. Subjects who initiated treatment but withdraw from the study will be used in the intent to treat analyses. In the past year, the Wilmot Cancer Institute had 75 patients that would be eligible for this study which demonstrates our ability to reach our accrual goal. To reach this goal of 30 fully evaluable subjects, the total number of subjects approached and/or consented may reach 75 subjects.

PARTICIPANT POPULATION(S)

Accrual Number:	Category/Group: (Adults/Children Special/Vulnerable Populations)	Consented: Maximum Number to be Consented or Reviewed/Collected/ Screened	Intent to Treat: Number to enroll and initiate treatment.	Fully Evaluable: Number to enroll and fully complete study.
Local	75/0/0	75	36	30
Study-wide	75/0/0	75	36	30
Total:	75/0/0	75	36	30

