7. SUBJECT WITHDRAWALS

Subjects will be advised during the consent process that they have the right to withdraw from the study at any time without prejudice or reason. Subjects that withdraw from the study will be replaced with another subject. Subjects will continue to receive radiation therapy as prescribed with standard of care with their treating radiation oncologist. The reason for discontinuation will be recorded in the subject's medical records. The date of occurrence and reasons for any subject withdrawal will be recorded and documented on the **Withdrawal Form**.

Subjects can be withdrawn from the study by the investigator or radiation oncologist for: non-compliance to study procedures; termination of funding; allergic reaction to Silverlon® dressing; worsening of the disease under study; intercurrent illness; pregnancy; or progression of skin reaction to RTOG score ≥3 in the radiation area where the Silverlon® dressing has been applied (i.e., whole breast). RTOG score ≥3 requires patients to have areas moist desquamation outside of skin fold regions (i.e., which would exclude inframammary fold and axillas because these are skin fold regions). Additionally, an area of moist desquamation that is >50% of the radiation treatment area (i.e., RISRAS-HPA score ≥3). Therefore, a large area of moist desquamation outside of skin folds would suggest withdrawal. Pinpoint areas and fold areas of moist desquamation could not require withdrawal. Patients withdrawn from the study will stop using Silverlon® dressing, but continue to receive radiation therapy on their normal schedule as prescribed by the treating radiation oncologist. For patients withdrawn from the study, standard of care for radiation dermatitis will be provided by the treating radiation oncologist, who will continue to follow the patient as per their normal clinical routine. The date of occurrence and reasons for any subject withdrawal will be recorded and documented on the Withdrawal Form. An adverse event will be reported if the skin reaction is RTOG ≥4. This grade of radiation dermatitis is severe and should be reported on the AE Source Doc and following reporting procedures stated in §10. Allergic reaction to Silverlon® dressing will be reported as an unexpected side effect on the AE Source Doc.

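### The lead compliance figure comes from the 30 completers, a set that stopping the dressing removes a subject from, so it is liable to be high by selection; the planned all-initiator analysis should lead

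*Combined protocol and SAP*

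**What the plan says.** Section 1.3 gives the feasibility objective two measures: compliance, and the rate of withdrawal because of the dressing.

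- **Analysis set for compliance (13.2).** "Compliance will be evaluated in the 30 fully evaluable subjects". Compliance is based on days worn during and after radiotherapy. The expected rate is 97%, taken from a cited breast-cancer trial.
- **Who is fully evaluable (3.1).** The definition includes starting the dressing and continuing it to two weeks after radiotherapy. "Therefore, the 30 fully evaluable subjects must complete full protocol procedures".
- **Withdrawal and replacement (7).** "Subjects can be withdrawn from the study by the investigator or radiation oncologist for: non-compliance to study procedures", among other grounds. No level of non-compliance is given. "Subjects that withdraw from the study will be replaced with another subject".
- **The second compliance analysis (13.2).** "Although we can and will evaluate compliance in all subjects that initiated treatment, these analyses will not provide a complete picture of compliance", the stated reason being early termination. Section 13.1 agrees: "In subjects that withdraw from the study, we will be able to partially evaluate compliance because of their early termination".
- **Withdrawn subjects (3.1).** "Subjects who initiated treatment but withdraw from the study will be used in the intent to treat analyses".
- **Precision (13.1).** Compliance has one row, at n = 30. The adverse-event measure has rows at both 30 and 36. Withdrawal has a row at 36.

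**The concern.** Compliance is meant to show whether patients will keep wearing the dressing. A subject who gives it up before the end cannot be fully evaluable under 3.1, whether or not anyone formally withdraws her. A subject who wears it poorly can also be taken off study under section 7. In both cases she leaves the lead compliance set, and recruitment continues until 30 others have finished. Membership of the set therefore depends on the outcome, and the expected direction of the bias is upward.

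The second feasibility measure does not fully close the gap. It is evaluated in everyone who started, but it counts withdrawals due to the dressing. Section 7 lists non-compliance and allergic reaction as separate grounds, and no rule says whether a withdrawal coded as non-compliance is attributed to the dressing. Such a subject could be missing from the lead compliance figure and also not counted as a dressing-related withdrawal.

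Section 14 says composite results will support a 510(k) application. A feasibility claim resting on a completer percentage is open to this challenge.

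**Working it through.** **Inputs.** From the table in 13.1: 29 of 30 completers compliant, 36 starters, 6 withdrawals, and exact two-sided 95% Clopper-Pearson intervals. The number k of the 6 withdrawn subjects who would count as compliant is not in the documents; it is an assumption, varied over its full range. The plan sets no per-subject threshold that turns days worn into a compliant subject, so the 29-of-30 count is the plan's own framing and is used as it stands.

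**Formula.** For x of n, the lower limit is the 0.025 quantile of Beta(x, n − x + 1) and the upper limit is the 0.975 quantile of Beta(x + 1, n − x).

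**Step 1: reproduce the plan.** 29/30 = 0.967, interval 0.828 to 0.999. This matches the compliance row. The withdrawal row also reproduces: 6/36, 0.064 to 0.328.

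**Step 2: move to all initiators.** The proportion is (29 + k)/36, and the gap is 96.7% minus that proportion.

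| k of 6 withdrawn counted compliant | All-initiator compliance | 95% CI | Gap (points) |
|---|---|---|---|
| 0 | 29/36 = 80.6% | 64.0–91.8% | 16.1 |
| 3 | 32/36 = 88.9% | 73.9–96.9% | 7.8 |
| 5 | 34/36 = 94.4% | 81.3–99.3% | 2.2 |
| 6 | 35/36 = 97.2% | 85.5–99.9% | none |

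**Step 3: why the denominator has to be stated.** Assume equal planned wear days per subject, completers wearing the dressing on 97% of days, and 6 subjects stopping halfway after 97% wear up to that point. In units of one subject's planned days, days worn are 30 × 0.97 + 6 × 0.5 × 0.97 = 29.10 + 2.91 = 32.01.

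- Over observed days only: 32.01 / (30 + 3) = 97.0%.
- Over planned days: 32.01 / 36 = 88.9%.

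The same data give answers 8.1 points apart, and the plan does not say which denominator applies to the all-initiator analysis.

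**The case against.** The plan is not blind to withdrawn subjects. It commits to compliance in all who started, and it says openly why it regards that result as incomplete. Feasibility also has a second measure that uses all starters, so subjects who withdraw because of the dressing are counted there. Compliance is a descriptive secondary measure with no threshold, test or decision attached to it. These points stand, and they limit the concern to which set leads and how later days are counted.

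Four stronger readings are tempting, and the documents do not support them.

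- *The compliance result is high.* Withdrawal for non-compliance is discretionary, and other grounds include skin progression, illness, pregnancy and funding. The fully evaluable definition sets no minimum wear, so a poor complier who stays to the end remains in the 30. The gap can be zero.
- *Intolerance and refusal are both removed from the feasibility assessment.* Withdrawal due to the dressing is evaluated in all starters, so this intolerance is visible there. Only withdrawals coded otherwise may be lost.
- *The 97% can be met however many subjects stop.* The plan foresees 36 starters and at most 75 consented. The replacement sentence also follows the text on voluntary withdrawal; extending it to investigator withdrawals is an inference, though the fixed target of 30 completers supports it.
- *A subject who wears the dressing for a few days and then quits scores 100%.* That is one possible reading. The plan gives a count of days and no denominator, so it does not fix any score for her.

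It can also be objected that section 7 has withdrawn subjects stop the dressing, so scoring later days as not worn after an RTOG ≥3 or allergic-reaction withdrawal would penalise subjects who followed the protocol. That is fair: it is a choice of estimand, and the fix treats it as one.

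**Conclusion.** The point holds in this form: the lead compliance set is selected partly on compliance, so its figure is liable to be high. The all-initiator analysis that would show the effect is planned but subordinate and under-specified. With the plan's 36 starters and 6 withdrawals, the overstatement lies between 0 and about 16 points. The upper end assumes that none of the 6 counts as compliant; the lower end assumes that all do. Neither end is a forecast, because the documents do not say how many subjects would leave for non-compliance. The range also rests on 29 of 30 completers being compliant, as the plan expects. This is an inexpensive improvement to a secondary measure and does not affect the primary safety analysis.

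**What to change.** In 13.2:

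- Make the all-initiator analysis the lead compliance result. Use as denominator each subject's planned wear days, from the start of radiotherapy to 14 days after its scheduled end.
- Count planned days as not worn after voluntary stopping, or after withdrawal for non-compliance or discomfort.
- Censor at the withdrawal date when the reason is unrelated to the dressing, such as pregnancy, intercurrent illness or loss of funding.
- For withdrawal because of RTOG ≥3 or allergic reaction, where the protocol itself ends dressing use, show the result both ways: later days not worn, and censored.
- Report withdrawals for non-compliance on their own line, so that they cannot be missing from both feasibility measures.
- Keep the 30-subject figure as supportive, labelled as compliance among completers.

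In 13.1, add a compliance row at n = 36 showing the range 29/36 to 35/36 with its intervals.

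**Cost.** Wording in two sections and one derived variable. The Compliance Log already records wear, and the Withdrawal Form already records the time and reason for leaving. The scheduled end date of radiotherapy is needed for withdrawn subjects and is not among the fields listed for the EndRT Data Form in 5.3, so it would have to be captured. The headline compliance figure may be less favourable.
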